6.1 STUDY PROCEDURES

6.1 Schedule of Assessments

A Cycle is defined as 4 weeks. Patients will be evaluated according to the schedule in Table 1.

Table 1. Schedule of assessments

Assessment	Screening ¹	Treatment cycles ²									Off Treatment ⁷	Follow Up ⁹
		Cycle 1	Cycle 2	Cycle 3	Cycle 4	Cycle 5	Cycle 6	Cycle 7	Cycle 8			
Informed consent	X											
Tissue collection consent	X											
Demographics	X											
Medical history	X											
Concomitant Medications	X		X	X	X	X	X	X	X	X	X	
Review of Systems	X		X	X	X	X	X	X	X	X	X	
Physical exam ²	X		X	X	X	X	X	X	X	X	X	
Vital signs ³	X		X	X	X	X	X	X	X	X	X	
Adverse event recording			X	X	X	X	X	X	X	X	X	X
Height	X											
Weight	X	X	X	X	X	X	X	X	X	X	X	
ECOG PS	X		X	X	X	X	X	X	X	X	X	
CBC with differential ⁶	X			X							X	
Serum Chemistry ^{4,6}	X		X	X	X	X	X	X	X	X	X	
Fasting Lipids ^{5,6}	X			X							X	
PSA ⁶	X	X	X	X	X	X	X	X	X	X	X	
Testosterone ⁶	X	X	X	X	X	X	X	X	X	X	X	
HgbA1c	X			X							X	
Vitamin B12	X										X	
CT CAP with IV contrast ⁸	X											
Bone scan*	X											
Research blood	X			X							X	
Research blood, optional	X			X							X	
FACT – P, version 4	X										X	
Survival & disease status ⁹												X

1. Physical examinations, blood tests must be performed within 2 weeks of treatment.
2. Evaluation is scheduled Day 1 of each cycle +/- 2 days to allow for logistical issues.
3. Vital signs include temperature, pulse, respiratory rate, and blood pressure
4. Albumin, alkaline phosphatase, total bilirubin, bicarbonate, BUN, calcium, chloride, creatinine, glucose, potassium, phosphorous, magnesium, total protein, SGOT, SGPT, sodium

15-1015

5. Cholesterol, LDL, HDL, Triglycerides.
6. All Labs (CBC, chemistries, fasting lipids, PSA, and testosterone) may be drawn up to 3 days prior to day 1 if site is unable to obtain results on day of treatment.
7. Off treatment evaluation should be scheduled at week 33 +/- 2 days to allow for logistical issues.
8. At physician discretion, a Chest x-ray can be done in place of a Chest CT at screening. Repeated bone or CT scans can be ordered during treatment if clinically indicated.
9. Follow up by telephone will occur once annually for 5 years, starting a year after the off-treatment visit +/- 2 months.

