6.3 Treatment Evaluations

Patients will be examined by the treating physician or designee on day 1 of each cycle prior to treatment. This examination will include a physical exam, toxicity assessment, concomitant medication review, and performance status. The physical exam must not occur more than 14 days prior to day 1 treatment. Chemistries, PSA, testosterone will be performed every 4 weeks, prior to each cycle. All required labs (such as CBC, chemistries, lipids, PSA, testosterone, etc) may be drawn up to 3 days prior to day 1 if site is unable to obtain results on day of treatment.

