6.4 End of Study and Follow up

Patients will have an evaluation and physical examination when they are taken off study treatment or complete study treatment (week 33). The reason for ending study treatment must be described in the source document and in OnCore. This evaluation will include a physical examination (including weight and vital signs), ECOG performance status score, CBC with differential and platelet counts, serum chemistry profiles, PSA, testosterone, HgbA1c, fasting lipids, research blood collection and toxicity assessment. Patients will be contacted every 12 months (+/- 2 months) to collect survival information, disease status, and the presence of persistent AEs for the next 5 years.

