7.0 MEASUREMENT OF EFFECT

7.1 Definitions of Biochemical Response and Progression

7.1.1 Complete Response: PSA <0.2 ng/mL confirmed on two consecutive

26

additional determinations taken at least 4 weeks apart.

7.1.2 *Partial Response:* A reduction in PSA $\geq 50\%$ from baseline without evidence of clinical or radiographic progression confirmed on two consecutive additional determinations taken at least 4 weeks apart.

7.1.3 *Stable Disease:* Patients who do not meet the criteria for response (CR or PR) or serological progression for at least 3 months (90 days) will be categorized as having stable disease.

7.1.4 *Progressive Disease:*

1) For patient who achieved a $\geq 50\%$ decline in PSA, progression is defined as an increase in PSA value by 50% above baseline or nadir (whichever is lowest), confirmed by a second PSA rise at least two weeks later. The PSA rise must be at least 5 ng/mL. Changes in PSA below 5 ng/mL will not be considered assessable for progression.

2) For patients with an undetectable PSA nadir (< 0.2 ng/mL), progression is defined as a PSA rise to the detectable range (detectable PSA is ≥ 0.2 ng/mL) confirmed by a second PSA rise at least 2 weeks later.

3) For patients whose PSA has not decreased by 50%, progression is defined as an increase in PSA value $\geq 50\%$ of baseline (on trial) or nadir PSA, whichever is lowest, confirmed by a repeat PSA at least 2 weeks later. The PSA must have risen by at least 5 ng/mL.

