11.3 Secondary assessments

We will test the hypothesis that the fraction of arm A and arm B patients with at least 85% reduction in PSA at 32 weeks will be the same. We will sort the 66 patients 32 week PSAs into groups above or below their grand median 32 week PSA. We will then submit the doubly dichotomized data to Fisher's exact test. The test will distinguish an odds ratio of 3.19 from one of 1.0 with 80% power and at most 10% type I error.

We will characterize the time to PSA progression and the time to onset of metastatic disease using the method of Kaplan and Meier. We will compare arms A and B for each of these end points with log-rank tests. Patients will be followed for PSA progression and for onset of metastatic disease for at least 60 months.

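### Section 11.3 promises at least 60 months of follow-up for PSA progression and metastasis, but no PSA is scheduled after week 33 and no scan after screening

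*Combined protocol and SAP*

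**What the plan says.** Section 11.3 analyses time to PSA progression and time to onset of metastatic disease by Kaplan-Meier and log-rank test, and adds: "Patients will be followed for PSA progression and for onset of metastatic disease for at least 60 months".

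Section 7.4 counts from randomization to the first confirmed PSA rise that meets the progression criteria after bicalutamide starts, or to clinical progression. Section 7.1.4 requires confirmation at least two weeks later and has three rules:

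- Rule 1 (decline of 50% or more): a rise of 50% over the lower of baseline and nadir, and of at least 5 ng/mL. It adds: "Changes in PSA below 5 ng/mL will not be considered assessable for progression".
- Rule 2 (nadir below 0.2 ng/mL): "progression is defined as a PSA rise to the detectable range".
- Rule 3 (no 50% decline): a 50% rise, again with a minimum of 5 ng/mL.

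The assessments are these:

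- On treatment (6.3): "Chemistries, PSA, testosterone will be performed every 4 weeks, prior to each cycle".
- End of treatment (6.1, footnote 7): "Off treatment evaluation should be scheduled at week 33". Section 6.4 lists PSA at that visit.
- Afterwards (6.1, footnote 9): "Follow up by telephone will occur once annually for 5 years, starting a year after the off-treatment visit". Its purpose in 6.4 is "to collect survival information, disease status, and the presence of persistent AEs for the next 5 years". Section 5.9 gives five years from end of treatment as a maximum.
- Scans (6.1, footnote 8): scheduled at screening; after that, "Repeated bone or CT scans can be ordered during treatment if clinically indicated".

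Section 2.2 also lists change in PSA doubling time (PSADT) off treatment, which 7.6 calls exploratory.

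**The concern.** A 60-month log-rank comparison needs events that can be established and dated over 60 months. The protocol schedules the measurement that defines the event for about the first eighth of that time. Later events would depend on which tests each man happened to have locally and on whether anyone recorded the dates. Metastasis has a similar gap, because no imaging is scheduled after screening.

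The event definition raises a second question. The PSA rise that counts as progression depends on whether the man reached an undetectable nadir, and that is the outcome arm B is hypothesised to improve (40% against 20% in 11.1). A better responder can be counted as progressed before a worse responder who is regrowing at the same rate.

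At stake are the interpretation of two secondary endpoints and one exploratory one.

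**Working it through.** Section 11.3 gives no event number, power or significance level for these log-rank tests, so there is no stated figure to reproduce.

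**1. How much of the 60 months has scheduled PSA**

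- Day 1 of cycle n falls in week 4(n − 1) + 1, so cycle 3 is week 9 and cycle 8 is week 29. The off-treatment PSA is at week 33.
- Week 33 is 33 × 7 / 30.4375 = 7.6 months, and 7.6 / 60 = 13%.
- The length of contact is not the obstacle. Five years after week 33 is about 67.6 months from the start. What is missing is the content of the contact. This reading rests on the prose of 5.9 and 6.4 and on footnote 9, not on column alignment in Table 1.
- The last scheduled pair of PSAs is weeks 29 and 33. A rise first seen at week 33 has no scheduled confirmation, so a confirmed event needs its first rise by week 29.
- One scheduled off-treatment PSA cannot give an off-treatment doubling time.

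**2. How many confirmed events the schedule can yield**

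With bicalutamide from week 9, later PSAs fall at weeks 13, 17, 21, 25, 29 and 33. Section 9.2.8 instead equates cycle 3 with week 13. That contradicts the 28-day cycles and must be reconciled; a week-13 start would shorten the window by four weeks.

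Suppose regrowth starts at once from the nadir at a PSADT of 3 months (91.3 days), the fastest that 3.1.11 admits. Growth to week 29 is g = 2^(days / 91.3). Rule 2 is met if the nadir is at least 0.2 / g, and the 5 ng/mL rise if it is at least 5 / (g − 1).

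| Nadir week | Days to week 29 | g | Rule 2 nadir from | +5 ng/mL nadir from | Events of 66 |
|---|---|---|---|---|---|
| 25 | 28 | 1.24 | 0.162 | 21 | about 1–2 |
| 21 | 56 | 1.53 | 0.131 | 9.4 | about 3–4 |
| 17 | 84 | 1.89 | 0.106 | 5.6 | about 4–5 |
| 13 | 112 | 2.34 | 0.085 | 3.7 | about 5–8 |

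The last column is a simulation on assumptions that the documents do not give: lognormal entry PSA (median 1, 2, 5 or 10 ng/mL, log SD 0.8, limited to 0.2–30); falls calibrated to 20% and 40% undetectable (log SD 1.0 or 1.5); lowest nadir 0.01 to 0.1; PSADT uniform over 3–12 months; 22 and 44 men. It leaves out men whose PSA never falls and clinical progression.

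Section 1.2 reports nadirs at 4 to 6 months for finasteride plus flutamide, which is weeks 26 to 35 counted from week 9. That is a different regimen, so it does not fix the nadir week here.

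For scale, with 2:1 allocation, two-sided 5% (assumed) and 80% power, the detectable hazard ratio is exp(−2.80 / √(d × 1/3 × 2/3)). With d = 10 events this is exp(−2.80 / 1.49) = 0.15.

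**3. The step in 7.1.4**

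Doublings needed = log2(threshold / nadir), where the threshold is 0.2 for a nadir below 0.2 and otherwise the larger of 1.5 × nadir and nadir + 5.

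| Nadir (ng/mL) | Threshold | Doublings |
|---|---|---|
| 0.01 | 0.2 | 4.3 |
| 0.10 | 0.2 | 1.0 |
| 0.19 | 0.2 | 0.07 |
| 0.21 | 5.21 | 4.6 |
| 1.0 | 6.0 | 2.6 |
| 10 | 15 | 0.58 |

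The jump at 0.2 follows from the text alone. Its effect on the arm comparison does not. In 64 assumed settings (20% against 40% undetectable, PSA monthly to 60 months), the hazard ratios B/A were:

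| Event rule | Equal regrowth | Arm B regrowth 1.3 times slower |
|---|---|---|
| 7.1.4 | 0.72–1.27 | 0.45–0.93 |
| +50% and +5 ng/mL for all | 0.62–0.85 | 0.40–0.53 |
| +50% alone for all | 0.99–1.01 | 0.49–0.50 |

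**4. Which rule applies**

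Most men with a nadir below 0.2 have also fallen by at least 50%, so they meet rules 1 and 2 together. Rule 1 would make their small rises not assessable, while rule 2 makes them events. Rule 2 reads naturally as the exception, but this is not stated.

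**The case against.** Follow-up does not end at week 33. Disease status is asked every year for five years, so a metastasis or a PSA result from routine care could be reported, and clinical progression counts under 7.4. The case report forms are not part of the documents and may ask for dates. This stands: a reader might infer that the 60-month comparison cannot be produced at all, and the documents do not support that. They support only that it cannot be produced from scheduled tests and that the protocol does not specify the data it would need.

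On the event count, a reader might infer that only one or two confirmed events are possible, all through rule 2. That holds only for a week-25 nadir. A week-13 nadir of about 3.7 ng/mL could meet rule 1 by week 29, and it is compatible with entry PSA below 30.

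On 7.1.4, treating the loss of an undetectable PSA as progression is a stated definition, not an error. A reader might infer that it reverses a true benefit. In the assumed settings the hazard ratio passed 1 only when regrowth was equal in both arms, and never when arm B regrew 1.3 times more slowly, although the trial hypothesises an enhanced antitumor effect. Dilution is small or absent if undetectable nadirs are very low (0.01–0.02). With equal undetectable rates there is no material type I error inflation. The comparison rules are not neutral either: a +5 ng/mL rise for all rewards a lower nadir, and +50% alone ignores nadir depth.

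**Conclusion.** The follow-up claim in 11.3 is wrong as written. PSA is scheduled for about 13% of the promised 60 months, and nothing in the protocol specifies dated PSA or imaging afterwards. Confirmed 7.1.4 events after week 33 and the off-treatment PSADT therefore cannot be established from scheduled data. This rests on the text alone.

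Scheduled confirmed PSA events by week 33 are likely to be few, roughly 1–2 to 5–8 of 66. That range depends on assumed nadir timing and depth, on a week-9 start of bicalutamide, and on leaving out men whose PSA never falls.

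The response-dependent threshold is secondary. The step at 0.2 ng/mL is certain. Dilution of the arm comparison is possible, but its size depends on assumed nadirs and regrowth and may be nil. It justifies a sensitivity analysis and does not show that the definition is invalid.

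The sponsor should correct the follow-up claim; the primary endpoint is untouched.

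**What to change.** 1. Preferred: add dated routine-care PSA values, imaging dates and the start of next therapy (itself a 2.2 endpoint) to the annual follow-up form for every man, whatever the reason treatment ended. Analyse PSA progression with a method that allows for irregular assessment times, such as interval censoring, and state how next therapy before an event is handled.
2. Otherwise: limit the PSA-progression and PSADT analyses to scheduled PSAs through week 33, report them descriptively, and remove the 60-month PSA claim and the off-treatment PSADT claim.
3. In either case, align the minimum of 60 months in 11.3 with the five-year maximum in 5.9, and reconcile the week given for cycle 3 in 9.2.8 with the 28-day cycles.
4. Pre-specify, beside the 7.1.4 analysis, a sensitivity analysis with one event rule for every man, the rule to be chosen by the investigators. State for analysis whether rule 2 overrides rule 1. The sponsor should reconcile this with the use of progression in 5.6; no treatment rule is proposed here.

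Cost: a few form fields, one added analysis, some work on the analysis method, and wording in 5.9, 7.1.4, 7.4, 9.2.8 and 11.3 (and in 2.2 and 7.6 under option 2). No added procedures. Downsides: routine-care PSA timing is irregular, the week-33 option leaves few events, and any common rule either depends on nadir depth or is noisy at very low PSA.

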11.4 Definition of Populations for Analyses

All Treated Subjects: all subjects who are treated with bicalutamide (arm A) or bicalutamide and metformin (Arm B). All Randomized Subjects: all subjects who received treatment.

11.5 Safety Analyses

Safety analyses will be conducted on treated patients. All adverse events will be summarized 1) without regard to causal relationship and 2) by causal relationship to study drugs, based on the Investigator's opinion. Worst toxicity grades per subject will be tabulated for selected adverse events and laboratory measurements. Any serious adverse event or

adverse event resulting in premature and permanent discontinuation of any study drug will be described in detail. Adverse events and other symptoms will be graded according to the National Cancer Institute (NCI) Common Terminology Criteria for Adverse Events (CTCAE) Version 4.0

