2.0 OBJECTIVES

2.1 Primary endpoint:

The proportion of patients with undetectable PSA (< 0.2 ng/mL) at 32 weeks with metformin plus bicalutamide compared to bicalutamide monotherapy.

2.2 Secondary endpoints:

- The proportion of patients with PSA decline > 85% at 32 weeks with metformin plus bicalutamide compared to bicalutamide monotherapy.
- The time to PSA progression with metformin plus bicalutamide compared to bicalutamide monotherapy.
- To evaluate the time to onset of radiographic evidence of metastatic disease (rPFS) with metformin plus bicalutamide compared to bicalutamide monotherapy.
- To characterize the PSADT changes pre-study, during treatment, and off treatment.
- To evaluate the safety and tolerability of metformin in this patient population.
- To evaluate QOL with metformin plus bicalutamide compared to bicalutamide monotherapy.
- To evaluate the time to next therapy (i.e. antiandrogen or GnRH antagonist/agonist).

2.3 Exploratory endpoints:

- Immunogenicity of bicalutamide +/- metformin by flow cytometric analysis of T-cell frequency, activation status, cytokine profiles, antibody levels and analysis of sCD27 and sCD40L
- Evaluate circulating PSA levels and correlations with immunogenicity and/ or efficacy

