5.3 Study Treatment

Upon initiation of treatment, both agents will be administered orally at the assigned doses and schedules. One cycle = 28 days = 4 weeks. Treatment will be administered on an outpatient basis.

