5.3.2 Treatment ARM B

Cycles 1 - 2: In order to minimize gastrointestinal discomfort, metformin dosing will be ramped up over a period of 2 weeks. Metformin treatment will

be started at 500 mg BID (Dose Level -2) and increased by an increment of 500 mg daily every week +/- 2 days provided no grade 2 or higher gastrointestinal toxicity is noted. If grade 2 or greater gastrointestinal toxicity occurs during the first 4 weeks of treatment, the subject will be evaluated every 2 weeks until resolution of toxicity to grade 0 or 1 and, then, the metformin dose will be increased to the next dose level. The target dose of metformin is 1000 mg BID. If patient cannot tolerate higher dose, metformin will continued at maximum tolerated dose as listed below.

Dose level	Metformin dose
Dose Level -2 (Week 1 +/- 2 days)	500 mg twice daily
Dose Level -1 (Week 2 +/- 2 days)	500 mg breakfast / 1000 mg at bedtime
Dose Level 0 (Week 3 and later)	1000 mg twice daily

Cycles 3 – 8: Continue metformin at maximum tolerated dose (up to 1000 mg BID). Start bicalutamide 50 mg/daily, orally, on a continuous basis to the end of study (week 32).

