9.2.4 Molecular Formula: C₁₈H₁₄N₂O₄F₄S

9.2.5 Mode of Action: Competitive inhibitor of androgen binding to cytosolic androgen receptors.

9.2.6 How Supplied: White, film-covered oral tablet containing 50 mg of bicalutamide. It will not be provided by the study (Commercial supply)

9.2.7 Storage: Controlled room temperature, 20-25°C.

9.2.8 Dose Specifics: 50 mg/daily orally beginning Cycle 3 (week 13), continuously to the end of study (please see Section XXX). The tablet should be taken at approximately the same time every day.

9.2.9 Route of Administration: Oral, may be taken with or without food.

9.2.10 Side Effects:

The most serious side effect that has been associated with bicalutamide is severe liver injury, which has been reported in approximately 1% of patients in controlled clinical trials. Hepatotoxicity typically occurs within the first three to four months of continuous treatment. It is not known whether the regimen used in this trial can cause liver injury. Transaminase levels will be drawn every 4 weeks. Other common side-effects of bicalutamide overlap those of leuprolide acetate, including hot flashes, generalized pain, asthenia, constipation, diarrhea, nocturia, testicular atrophy, and gynecomastia.

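### Read literally, the safety set leaves out arm B men who take metformin but leave before ever starting bicalutamide, which can hide early metformin toxicity

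*Combined protocol and SAP*

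**What the plan says.** Section 11.5 sets the safety population in one sentence: "Safety analyses will be conducted on treated patients". It does not refer back to a named set. Section 11.4, directly before it, has one definition with treated in its name: "All Treated Subjects: all subjects who are treated with bicalutamide (arm A) or bicalutamide and metformin (Arm B". It then adds a second set: "All Randomized Subjects: all subjects who received treatment".

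In arm B (section 5.3.2) metformin is taken alone in Cycles 1 and 2. For Cycles 3 to 8 the text continues metformin and adds: "Start bicalutamide 50 mg/daily, orally, on a continuous basis to the end of study (week 32". In arm A (5.3.1) Cycles 1 and 2 are observation with no drug.

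The secondary endpoints in 2.2 include: "To evaluate the safety and tolerability of metformin in this patient population". Section 11.5 also undertakes to describe in detail any adverse event that leads to permanent discontinuation of a study drug.

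**The concern.** The treated set in arm B is defined by having had both drugs, but the drugs start two cycles apart. A man who takes metformin, does badly on it and leaves before bicalutamide starts has been dosed and may have had the trial's most informative tolerability event. Yet he does not meet the definition. His adverse events and the reason he stopped would be absent from the tables meant to answer the metformin safety objective.

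The excluded window is also the one that matters most for metformin. It contains the dose ramp-up, and section 1.3 says that gastrointestinal effects occur in more than 1 in 10 patients and are usually transient when treatment is started. Entry to the set therefore depends partly on the outcome being measured.

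**Working it through.** **1. The nearest figure in the plan.** The plan attaches no number to the safety set. The closest is the arm B DLT rule in 11.2, with nominal arm B sizes from 11.1 of 26 in the first cohort and 26 + 18 = 44 in total. Exact binomial tails:

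| Quantity | True DLT rate | Recomputed | Stated in 11.2 |
|---|---|---|---|
| P(X ≥ 5), n = 26 | 20% | 0.617 | over 57% |
| P(X ≥ 5), n = 26 | 5% | 0.0085 | less than 1% |
| P(X ≥ 7), n = 44 | 20% | 0.804 | at least 80% |
| P(X ≥ 7), n = 44 | 5% | 0.0059 (0.0118 if crossing either boundary counts) | about 1% |

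The stated properties reproduce with every arm B man in the denominator, and the wording of 11.2 counts arm B patients. The rule is not tied to the treated set.

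**2. The window.** Section 5.3 gives "One cycle = 28 days = 4 weeks". Cycles 1–2 last 2 × 4 = 8 weeks, so Cycle 3 begins in week 9. Section 9.2.8 instead has "50 mg/daily orally beginning Cycle 3 (week 13". Week 13 is 3 × 4 + 1, the first week of Cycle 4, and would make the metformin-only period 12 weeks. The passages conflict and must be reconciled, because they set the length of the window.

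**3. Who is in the set, applying 11.4 literally.**

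| Man | Drugs taken | In the treated set? |
|---|---|---|
| Arm B, metformin held and restarted, bicalutamide started | both | yes |
| Arm B, metformin stopped for good, bicalutamide started | both | yes |
| Arm B, metformin taken, leaves before Cycle 3 | metformin only | **no** |
| Arm A, leaves during observation | none | no |

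Nothing in 11.4 requires metformin to be ongoing when bicalutamide starts. The documents do not say whether a man who stops metformin permanently may go on to bicalutamide alone.

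**4. Can the third row occur?** Yes. Section 5.5 withdraws men who do not recover from treatment-related toxicity within 4 weeks, and removes those whose treatment is delayed by more than 4 consecutive weeks. Section 5.5.1 lets men who cannot tolerate the ramp-up go off study treatment. Section 5.6 ends treatment for unacceptable adverse events. A stop at the end of the 2-week ramp-up plus a 4-week delay reaches week 6 (2 + 4), inside the 8-week window.

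**5. Direction and size.** Let x of n arm B men have a given toxicity, and let k of those x leave before bicalutamide. The table shows (x − k)/(n − k) instead of x/n. The difference is

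x/n − (x − k)/(n − k) = k(n − x) / [n(n − k)],

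which is never negative. For exits caused by toxicity, the error therefore goes one way. Early exits by men without the event would shrink the denominator only, and so push the other way.

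The documents give no value for k, so the values below are assumptions, with n = 44:

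| k (assumed) | Lead-in toxicity stops, all dosed men | Same, literal set | Any toxicity with x = 7 (assumed; 7/44 = 15.9%), literal set |
|---|---|---|---|
| 2 | 2/44 = 4.5% | 0/42 | 5/42 = 11.9% |
| 4 | 4/44 = 9.1% | 0/40 | 3/40 = 7.5% |
| 6 | 6/44 = 13.6% | 0/38 | 1/38 = 2.6% |

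The third column is zero for every k: the literal set cannot show a stop that happened before bicalutamide and was never followed by it.

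**The case against.** The strongest reply is that 11.5 never invokes 11.4. It speaks of treated patients in lower case, and the second definition in 11.4 uses treatment in a looser sense. Section 4.1 requires protocol treatment to begin within 7 days of registration, and Table 1 lists Cycle 1 among the treatment cycles. An analyst could read treated as having received any study drug, and then nobody is lost. That reading is available, but it is not what the only treated definition says. A safety population should not depend on which of two neighbouring sentences the analyst follows.

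Second, these men are not lost to oversight. Adverse events go on case report forms and serious events are reported from the first day of treatment (10.2), and the monitoring board reviews toxicity at least every 6 months (12.2). This is correct, and it limits the harm to patients. It does not repair the final tables.

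Third, early loss may be small. Section 5.5.1 steers men towards holding, restarting and re-challenge, and the neoadjuvant study of 24 men described in 1.5 reported no grade 3 events over a median of 41 days on metformin. That is fair, and is why no effect size is claimed here.

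Three stronger readings may tempt a reader, and the documents do not support them. One is that every man who stops metformin in the first 8 weeks drops out; the trigger is never starting bicalutamide. Another is that the DLT rule loses its ability to detect toxicity; 11.2 counts arm B patients without reference to the treated set. The third is that omitting arm A men who leave during observation is an equal fault; they have taken no study drug, and including them is a matter of preference.

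**Conclusion.** The point holds in a limited form. On the literal text, arm B men who take metformin and leave before bicalutamide fall outside the safety tables. To the extent that they leave because of toxicity, metformin's reported tolerability is biased in its favour. This rests on two things: that 11.5 means the treated set in 11.4, which is the natural but not the only reading, and that some men leave in the lead-in, which the protocol provides for but does not quantify. With 2 to 6 such men among 44 (assumed), between 4.5% and 13.6% of arm B would be toxicity stops that the tables could not show.

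This point does not bear on the primary endpoint, and the DLT rule stands as written. It should be settled before the safety tables are produced, as a correction of a definition rather than a fault that puts the trial in doubt.

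**What to change.** In 11.4, define a safety set as every man who took at least one dose of metformin or bicalutamide, and have 11.5 cite it by name. Tabulate arm B adverse events and discontinuations from the first metformin dose. Show Cycles 1–2 separately from Cycles 3–8, so that the metformin-only period is visible and the period when both arms take bicalutamide can be compared on its own.

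In the same edit, reconcile the All Treated and All Randomized definitions, since the second is also worded in terms of treatment received. Reconcile the start of Cycle 3 between the 28-day cycle (week 9) and 9.2.8 (week 13). Section 11.2 needs no change on this account.

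The cost is a revised definition and one extra split in the tables. No new data are needed: 10.2.1 already records all adverse events, and 6.4 includes a toxicity assessment when a man comes off study treatment. The only downside is that reported toxicity may be slightly less favourable.
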